**Table 5–2: Calculation rules for duration (days) of AEs (applicable also to ADEs)**

Data Availability	Onset Date/Time	Outcome Date/Time	Calculation Rules
Complete data	D1/T1	D2/T2	Duration = $[(D2 - D1) * 24 + (T2 - T1)]/24$ d
End time missing	D1/T1	D2/--	End time is substituted by time 23:59h (=23.98 in decimal format). Duration = $< [(D2 - D1) * 24 + (23.98 - T1)]/24$ d
Start time missing	D1/--	D2/T2	Onset time is substituted by 00:00h. Duration = $< [(D2 - D1) * 24 + T2]/24$ d
Start and end time missing	D1/--	D2/--	Duration = $< (D2 - D1) + 1$
Start day and time missing	--/--	D2/T2	Duration = $< [(D2 - D0) * 24 + (T2 - T0)] / 24$ d For a participant in the SS, D0 and T0 are the date and time of dosing and for screen failures, D0 = the Screening Visit date and T0 = 0.
End day and time missing	D1/T1	--/--	For ongoing AE duration = > Discharge day – D1 d For resolved AE duration = < Discharge day – D1 d Where Discharge Day refers to the date of the SFU Visit or date of discontinuation. For any AEs with known start date/time after the date of discontinuation, the date of last contact will be used as the discharge day.
Start and end date missing	--/--	--/--	For ongoing AE duration = > Discharge day – D0 d For resolved AE duration = < Discharge day – D0 d Where Discharge Day refers to the date of the SFU Visit or date of discontinuation. For a participant in the SS, D0 is the date of dosing and for screen failures, D0 = the Screening Visit date.

ADE=Adverse Device Effect; AE = Adverse Event; SS=Safety Set

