### **8.3.1        Time period and frequency for collecting AE and SAE information**

All AEs and SAEs will be collected from the signing of the ICF and at the time points specified in the schedule of activities (Section 1.3).

In order to ensure complete safety data collection, all AEs occurring during the study (ie, after the signing of the ICF), including any pretreatment and posttreatment periods required by the protocol, must be reported in the CRF even if no study medication was taken but specific study procedures were conducted. This includes all AEs not present prior to the initial visit and all AEs that recurred or worsened after the initial visit.

All SAEs will be recorded and reported to the Sponsor or designee within 24 hours, as indicated in Appendix 4 (Section 10.4). The Investigator will submit any updated SAE data to the Sponsor within 24 hours of it being available.

The Investigator is specifically requested to collect and report to UCB (or its representative) any SAEs (even if the Investigator is certain that they are in no way associated with the IMP), up to 30 days from the end of the study for each study participant, and to also inform study participants of the need to inform the Investigator of any SAE within this period. Serious AEs that the Investigator thinks may be associated with the IMP must be reported to UCB regardless of the time between the event and the end of the study.

The method of recording, evaluating, and assessing causality of AE and SAE and the procedures for completing and transmitting SAE reports are provided in Appendix 3 (Section 10.3).

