## **9.5 Planned safety and other analyses**

### **9.5.1 Safety analyses**

All safety parameters will be listed by study participant and treatment group using the Safety Set. The incidence of TEAEs will be determined by treatment group, where applicable. Absolute and relative frequencies for a given TEAE by preferred term as per the Medical Dictionary for Regulatory Activities (MedDRA®, version 19.0) will be determined within each treatment group and system organ class. Additional tables will summarize TEAEs by maximum event intensity and causal relationship with IMP per treatment group and overall. The actions taken for each

TEAE, the time of onset of the TEAE after dosing, and the duration of each AE will be listed. The TEAEs leading to discontinuation and SAEs will also be summarized.

For continuous laboratory variables, values and changes from Baseline will be summarized at each time point. For categorized values according to the reference range, shift tables from Baseline to each postdose time point will be presented for selected variables. Values outside the reference range will be flagged in the data listings. The reference ranges will be reported.

Normal versus abnormal findings for the various ECG parameters and overall ECG will be analyzed as required, focusing on the identification of outliers and of any trends for changes following administration of IMP with respect to QT/QTc. Descriptive statistics will be presented for ECG value and changes from Baseline over time.

Descriptive statistics will be reported for all vital sign measurements (including systolic and diastolic BP, pulse rate, and tympanic body temperature). Measured values and changes from Baseline will be summarized for all study participants by time point.

Abnormal findings in the physical examination will be presented in listings only.

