- If the start date is completely unknown, then use the date of dosing. If this results in an imputed start date that is after the specified end date, then use January 01 of the year of the end date, or the date of Screening if this is later (if the latter imputation results in an end date that is earlier than the start date, then use January 01). If the imputed date is the date of dosing then time will be imputed as the start time of the sc injection (i.e., event will be regarded as treatment-emergent).

Any medication with a start date on the dosing date and time unknown, will be assumed to be concomitant.

The following rules will be applied for partial stop dates:

- If only the month and year are specified, then use the last day of the month;

- If only the year is specified, then use December 31 of the known year;
- If the stop date is completely unknown, do not impute the stop date.

Missing or partially missing date and/or times will be imputed as described in [Table 5–2](#) for the calculation of duration of each AE. Adverse event duration is computed and reported in day and time format: xx d hh:mm.

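### When dates are missing, two rows of SAP Table 5–2 can print a negative AE duration or an unsupported minimum duration in the AE listing

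*SAP*

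**What the plan says.** SAP 5.1.1.2.4 handles incomplete dates in two separate ways.

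The first set of rules imputes partial start and stop dates. Its stated purposes are to classify AEs as treatment-emergent and medications as prior or concomitant. A wholly unknown start is set to dosing, but if that falls after the recorded end the rule moves it back: "use January 01 of the year of the end date, or the date of Screening if this is later". This set therefore checks the order of the dates.

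The second set is for AE duration: "Missing or partially missing date and/or times will be imputed as described in" Table 5–2, which also applies to adverse device effects (ADEs). Two of its rows matter here.

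- **Start day and time missing, end known.** Duration is shown as less than the end minus D0/T0. "For a participant in the SS, D0 and T0 are the date and time of dosing"; only screen failures get the Screening Visit date instead. Nothing compares D0 with the end date.
- **Start and end date missing.** The two branches are "For ongoing AE duration = > Discharge day – D0 d" and "For resolved AE duration = < Discharge day – D0 d". D0 is again dosing for anyone in the Safety Set. Discharge day is the date of the Safety Follow-Up (SFU) Visit or of discontinuation.

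Protocol 8.3.1 states: "All AEs and SAEs will be collected from the signing of the ICF". Protocol 9.5.1 requires that "the duration of each AE will be listed", and SAP 5.6.2 places duration in the by-participant listing of all AEs, not only TEAEs.

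**The concern.** Both rows treat dosing as if it were the known start of the event.

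In the missing-start row this fails for an event that began and ended between consent and dosing. Such events are recorded for participants who are later dosed, and the formula then subtracts a later time from an earlier one.

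In the both-dates-missing row, an ongoing event is given a minimum duration measured from dosing. If the event began after dosing, that difference is the longest it can have run by discharge, not the shortest. The resolved branch of the same row uses the same difference as an upper limit.

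At stake is the accuracy of a listing that the protocol requires. An impossible negative value would be noticed. A definite minimum of about 20 weeks for an event with no recorded dates might not be, and it overstates what is known.

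**Working it through.** **Inputs.** AE collection starts at consent (Protocol 8.3.1). Screening runs from Day -28 to Day -2, dosing is on Day 1 and the SFU Visit is on Day 140 (SAP 5.1.1.1.2), with a window of ±3 days (Protocol Table 1-1). There is no Day 0 (SAP 5.1.1.1.1). The formulas are those of Table 5–2. The calendar dates and clock times below are constructed for illustration.

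**The table's own constant.** 23:59 in decimal hours is 23 + 59/60 = 23.98, which matches Table 5–2.

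**Missing-start row.** The formula is [(D2 − D0) × 24 + (T2 − T0)] / 24.

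- Dosing 1 Sep 09:00, AE ended 27 Aug 12:00, start unknown: [(−5) × 24 + (12 − 9)] / 24 = −117/24 = −4.875 d, printed as < -4.9 d.
- With the screen-failure version of D0 (Screening Visit on 10 Aug, T0 = 0): [17 × 24 + 12] / 24 = 420/24 = 17.5 d, a usable upper bound.
- Over the pre-dose window, with dosing at 09:00 and the end at 10:00, the row gives −0.96 d for an end on Day -1, −9.96 d for Day -10 and −27.96 d for Day -28.

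**Both dates missing, ongoing.** The formula is Discharge day − D0.

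- For a completer seen on Day 140: 140 − 1 = 139, printed as > 139 d. Across the visit window the figure is 136 to 142 d.
- Time actually elapsed at the Day 140 visit, by true onset:

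| True onset | Elapsed at SFU (d) | Is > 139 d supported? |
|---|---|---|
| Day -20 | 159 | Yes |
| Day 1 | 139 | Yes, to the day |
| Day 30 | 110 | No |
| Day 60 | 80 | No |
| Day 100 | 40 | No |
| Day 130 | 10 | No |

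The printed minimum holds only for onset at or before dosing. With no start date, the record cannot show which case applies.

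**Comparison with the known-start row.** Where the start D1 is known and the event is ongoing, the table prints more than Discharge day − D1. That is sound to within a day, because D1 was observed. Putting D0 in its place keeps the sign but loses the observation behind it.

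**The case against.** The best defence of the second row is that it follows a convention used elsewhere in the SAP. A wholly unknown start is set to dosing for classification, and given that start the > sign only marks an event still running at discharge. The statement is also true for an event that began before dosing, and an ongoing event may in the end last longer than 139 d. All of this is correct, but none of it makes 139 d a supported minimum when the onset is unknown.

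On impact the defence is largely right. AEs are asked about repeatedly in-house, daily on Days 4 to 10 and at every later visit, and the data are cleaned before lock, so missing start dates should be few. Listings show dates as reported, so the blank date stands beside the printed duration. No summary of duration is planned.

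Three stronger readings are tempting, and the documents do not support them.

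- **A known month is thrown away, so the bounds are several times too loose.** The relevant rows show the missing date as wholly blank. The lead-in sends partial dates to the table, but the SAP never says that a known month is discarded. The tighter month rules are stated for classification, so leaving them unused is not a contradiction. A loose bound is also usually true: for a resolved event with onset on 3 Oct 10:00, an end some time in October and an SFU Visit on 18 Jan, < 107 d is correct even though 31 Oct 23:59 would give 28.6 d.
- **The TEAE endpoint is affected.** Treatment-emergent status is decided under the classification rules, not under Table 5–2.
- **The listing will contain such values.** It will only if such a record occurs, and the documents give no count of incomplete AE dates.

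**Conclusion.** The point holds for two rows: they are wrong as written. The missing-start row yields a negative duration for any Safety Set participant whose AE ended before dosing with no recorded start, from about −1 d to about −28 d over the screening window. The both-dates-missing row prints an unsupported minimum for an ongoing AE, about 139 d in a completer, which is false as time elapsed by discharge for any onset after dosing.

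This rests on applying the table literally to records that the protocol allows; the example dates are constructed. The effect is confined to durations in the AE listing, including those for ADEs, and the records are probably rare. TEAE counts, PK parameters and the bioequivalence conclusion do not depend on it. The change is worth making but not essential.

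**What to change.** **Missing-start row.** When the AE ended before dosing, take D0 as the Screening Visit (consent) date, as the table already does for screen failures. Use dosing as the start of a < bound only when the AE is known to have begun after dosing; otherwise use Screening.

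**Both-dates-missing row.** For an ongoing AE, print 'not calculable'. Keep the > form only where the start date D1 is known.

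**Optional tightening where a month is known.** Take the 1st of that month, or Screening if later, as the earliest start, and the last day of the month as the latest end. Two shortcuts should be avoided.

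- Do not reuse the classification rule that puts in dosing for the dosing month. With dosing on 15 Sep, start recorded only as September, true onset on 5 Sep and end on 20 Sep, it would print < 5 d (20 − 15) for an event of 15 d (20 − 5).
- Do not cap a resolved event's end at discharge, because Protocol Appendix 3 follows AEs until resolution, which may come after the SFU Visit.

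**Cost.** A few lines of SAP wording and a small change to the listing program, with no new data. The downside is that some listed durations become 'not calculable' or less tight.

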### 5.1.1.2.5 Impact of COVID-19

The FDA and EMA (see [Section 7](#)) have provided guidance to help assure the safety of study participants, maintaining compliance with good clinical practice (GCP), and minimizing risks to study integrity during the COVID-19 pandemic. One of the recommendations is a risk assessment of the impact of COVID-19 on study integrity and interpretability of potential study results. In particular, the major statistical principles need to be considered regarding the impact of COVID-19 on studies and how to handle missing or delayed assessments resulting from the pandemic. The impact of the COVID-19 pandemic, at the visit level, will be assessed by data collected on a specific COVID-19 impact CRF. Any dropouts due to COVID-19 will be handled

in the same way as dropouts for other reasons. Should one of the ongoing reviews of COVID-19 related PDs (see Section 5.1.1.4) suggest that the impact of COVID-19 is more significant than expected, the SAP may be updated to include details of strategies to handle missing data and/or sensitivity analyses.

### **5.1.1.3 Handling of repeated and unscheduled measurements**

All repeated and unscheduled measurements will be presented in the listings. Repeated and unscheduled measurements will not be used for statistical analysis or summary tables, unless the repeated measurement was performed due to technical reasons, or the repeated measurement occurred prior to IMP administration and is defined as the 'Baseline'. The following general rules will apply to all repeated and unscheduled measurements:

- For repeated measurements obtained prior to the IMP administration, the latest reported value (which may be scheduled or unscheduled) will be used in the calculation of descriptive statistics
- For repeated measurements obtained at any time point after dosing, the first reported value of any repeated measurements will be used in the calculation of changes from Baseline and for the descriptive statistics.

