**Table 1-1: Schedule of study assessments overview**

Assessments	Screening	Inhouse Treatment Period			Outpatient Visits			Early Withdrawal a / SafetyFollow-Up/ Visits
		Day -1	Day 1		Day 1 postdose to Day 3 postdose	Days 4 to 10	Days 13, 16, 19, 22, 25, and 28 (±1 days)	
	Day -28 to Day -2	Admission	Pre-dose	0 h				Day 140 (±3 day)

A=ambulatory; Ab=antibody; ADAb=antidrug-antibody; AE=adverse event; BKZ=bimekizumab; BP=blood pressure; COVID-19=coronavirus disease 2019; ECG=electrocardiogram; FSH=follicle stimulating hormone; h=hour; HBc-Ab=hepatitis B core antibody; HBsAg=hepatitis B surface antigen; HCV-Ab=hepatitis C virus antibody; HIV=human immunodeficiency virus; HIV1/2-Ab=HIV1/2 antibody; HIV1-Ag=HIV1 antigen; I=inhouse; IgG=immunoglobulin G; IgM=immunoglobulin M; IMP=investigational medicinal product; PK=pharmacokinetic(s); RT-PCR=real-time reverse transcriptase polymerase chain reaction; SARS-CoV-2=severe acute respiratory syndrome coronavirus 2; sc=subcutaneous; SFU=Safety Follow-Up; SOP=Standard Operating Procedure; TB=tuberculosis

Note: At the Investigator's discretion, an Unscheduled Visit may be completed at any time during the study but prior to the SFU Visit, if deemed necessary for the study participant's safety and well-being. The same assessments as performed on the SFU Visit, or alternatively as advised by the Investigator, should be performed if a study participant is attending an Unscheduled Visit during the study.

a If a study participant withdraws prior to completion of the study, an Early Withdrawal Visit will be conducted at the time of withdrawal and the same assessments planned for the SFU Visit will be performed.

b Refer to UCB g-q-100573 Tuberculosis Detection Procedure Guideline for details regarding TB infection status, detection procedures, and the related exclusion criteria.

c Randomization will occur prior to dosing on Day 1, provided all information for eligibility is known. The study identification card will be given to the study participant following IMP administration.

d Within 24 hours of the indicated visit study participants will be asked to record signs and symptoms of COVID-19 or any contact with persons having confirmed SARS-CoV-2 infection. In case of signs/symptoms or contact, the visit will be cancelled and reason for cancellation will be appropriately documented documented in the eCRF.

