e Bimekizumab will be administered as a sc injection as detailed in Section 6.1.

f A full physical examination will be performed at the Screening Visit, Day -1, and the Early Withdrawal/SFU Visit. On all other days (Days 2, 3, 9, 25, 56, 84, and 112) a physical examination is planned, it will be performed symptom-driven, ie, in case of an AE.

g Vital signs include BP, pulse rate, and tympanic body temperature. At outpatient visits without regular vital signs measurements, only tympanic body temperature will be collected. The number of readings to be collected will be determined by local SOPs at the sites.

h During the inhouse treatment period, vital signs and ECGs should be measured/taken prior to blood sampling, where applicable, with the study participant resting in the supine position for at least 3 minutes. Vital signs and ECGs will be measured on Day 1 at predose, at 1.5h, 5h, and 11h postdose, on Day 2 at 24h postdose, and on Day 3 at 48 hours postdose, then on Days 9, 25, 56, 84, 112, and 140.

i As this is a single-dose study, device presentation deficiencies are only to be captured on Day 1 (ie, the day when IMP is administered during the inhouse treatment period).

j Serology variables include HbsAg, HBc-Ab (both IgG and IgM), HCV-Ab, HIV1-Ab, HIV1-Ag, and HIV-2 Ab.

k The frequency of SARS-CoV-2 RT-PCR will be assessed in compliance site-specific procedures and local regulations.

l Blood sampling for hematology (including coagulation and hemostasis) and clinical chemistry will be performed at the Screening Visit, and Days -1, 2, 9, 25, 56, 84, 112, and the SFU Visit.

m Urinalysis via dipstick will be performed at Screening, Day-1, Days 2, 9, 25, 56, 84, 112, and 140.

n The PK sampling time points will be as follows: predose (within a maximum of 60 minutes prior to dosing), 1.5h, 5h, 24h, 48h postdose, and from Day 4 onwards at every visit (ie, Days 4 to 10, 13, 16, 19, 22, 25, 28, 56, 84, 112, and 140).

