All results, regardless of local or central laboratory or repeated or unscheduled values, will be listed. However, only scheduled results from the central laboratory will be used in the summary statistics. In addition, if data from central laboratory is missing and meant to be presented, and a

local value is available, the local value will not be included in the summary statistics as it may be biased.

Decimal places for descriptive statistics will always apply the following rules:

- “n” will be an integer
- Mean, SD, and median will use one additional decimal place compared to the original data
- CV [%] will be presented with one decimal place
- Min and max will have the same number of decimal places as the original value

Derived variables in general will display the mean, SD and median to 1 more decimal place than the variables used in the derivation. If the number of decimal places reported in the raw data is varied then use either the maximum raw number of reported decimal places or 3, whichever is the lowest, as a guide for the descriptive statistics.

If participants have more than one observation for a given time point, the observation closest to the intended time point will be used. If both observations are equidistant from the intended time point, then the later value will be used.

Data listings containing all documented data and all derived data will be generated.

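### A post-dose neutrophil or QTcF extreme seen only off schedule enters no laboratory or ECG table, and no table counts participants by their worst post-dose value

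*SAP*

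**What the plan says.** **Rule for tables.** SAP 5.1.1.3 sends all repeated and unscheduled values to the listings, then states: "Repeated and unscheduled measurements will not be used for statistical analysis or summary tables, unless the repeated measurement was performed due to technical reasons". The other exception is a pre-dose repeat that serves as Baseline. After dosing, "For repeated measurements obtained at any time point after dosing, the first reported value of any repeated measurements will be used in the calculation".

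**Extra rule for laboratory data.** SAP 5.1 says "only scheduled results from the central laboratory will be used in the summary statistics". If the central value is missing and a local one exists, "the local value will not be included in the summary statistics as it may be biased".

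**Table layout.** SAP 5.6.3.1 plans values, changes and shift tables for hematology at each post-Baseline time point. SAP 5.6.3.3 plans the QTcF categories, for value and for change, by visit or time point. Neither section has a row for a participant's worst post-dose value.

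**Off-schedule data are foreseen.** The note to protocol Table 1-1 says that, at the investigator's discretion, "an Unscheduled Visit may be completed at any time during the study", before the Safety Follow-Up (SFU) Visit. As to content: "The same assessments as performed on the SFU Visit, or alternatively as advised by the Investigator, should be performed". The SFU column of Table 1-1 includes hematology and ECG.

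**The concern.** An Unscheduled Visit is held for safety reasons and by default yields a neutrophil count and an ECG. The planned tables cannot use either. If that visit gives a participant's only extreme value, every by-time-point row shows that participant as unremarkable or absent.

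Three places in the documents suggest that such extremes are of interest. Protocol 8.3.6.1 names neutropenia as a prespecified safety topic. Protocol 9.5.1 directs the ECG analysis at QT/QTc outliers. SAP 5.6.3.1.1 already applies its liver criteria at any visit and summarises the participants who meet them. Neutrophils and QTcF have no counterpart to that liver output.

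What is at stake is the completeness of the tabulated arm comparison for two safety variables. A reader who wants the number of participants per arm with any post-dose extreme has to build it from listings.

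**Working it through.** The plan states no figure on this point, so the check is a reading of the outputs and a count.

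**1. Which outputs can hold an off-schedule extreme?**

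| Output | Off-schedule post-dose value used? | Participant count over all post-dose values? |
|---|---|---|
| Neutrophil values, changes and shifts (SAP 5.6.3.1) | No (5.1 and 5.1.1.3) | No, by time point |
| QTcF summaries and categories (SAP 5.6.3.3) | No (5.1.1.3) | No, by visit or time point |
| Liver criteria (SAP 5.6.3.1.1) | Criteria apply at any visit | Yes, but only ALT, AST and bilirubin |
| Listings, including out-of-range laboratory results | Yes | No |
| Adverse event tables | Only if judged clinically significant (protocol 10.3.1) | Yes, for recorded events |

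The exception for technical repeats does not cover a safety-driven unscheduled value. SAP 5.1 also says that, of several observations for one time point, the closest is used, which does not sit easily with the first-reported rule in 5.1.1.3. It could admit an unscheduled value only if that value were assigned to a scheduled time point, and the SAP defines no such assignment.

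**2. Scheduled post-dose time points.**
- Hematology, Table 1-1 footnote l: "at the Screening Visit, and Days -1, 2, 9, 25, 56, 84, 112, and the SFU Visit". After dosing these are Days 2, 9, 25, 56, 84, 112 and 140, so 7 time points. Nominal gaps are 7, 16, 31, 28, 28 and 28 days.
- ECG, footnote h: 1.5, 5, 11 and 24 h, "on Day 3 at 48 hours postdose, then on Days 9, 25, 56, 84, 112, and 140". That is 5 + 6 = 11 time points.

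From Day 25 onward, scheduled values of both kinds are nominally 28 to 31 days apart. An extreme seen only between them counts 0 at all 7 or all 11 time points.

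**3. Size per participant.** The planned arm is about 60, and these tables use the Safety Set. One participant is 1/60 = 1.7 percentage points. The documents give no rate of such cases, so k is an assumption:

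| k affected in an arm | Planned tables | Worst-post-dose row |
|---|---|---|
| 1 | 0/60 | 1/60 = 1.7% |
| 2 | 0/60 | 2/60 = 3.3% |
| 3 | 0/60 | 3/60 = 5.0% |

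**4. By-time-point rows do not add up to participants, even for scheduled data.** Suppose each time point shows one abnormal value in an arm. For neutrophils that could be 1 to 7 participants (1/60 = 1.7% to 7/60 = 11.7%). For QTcF it could be 1 to 11 (1.7% to 11/60 = 18.3%). The planned tables cannot tell these cases apart.

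**The case against.** The case for leaving the plan alone is substantial.

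- **By-time-point tables are what the protocol plans.** A reader might infer a departure from the protocol. There is none: protocol 9.5.1 itself specifies shifts at each post-dose time point and says the ECG findings are analysed as required. Laboratory and ECG data are other/exploratory endpoints.
- **The values are not hidden.** A reader might infer that they are lost. They are listed, out-of-range laboratory results are listed again, and ECG findings have their own listing. Clinically significant values are adverse events. Protocol 8.3.6.1 refers to special monitoring, additional data collection or enhanced signal detection for the safety topics, and protocol 8.4 allows periodic review of laboratory and ECG results. What remains is an extreme that the investigator saw and did not judge clinically significant.
- **The first-value rule usually keeps the extreme.** Under protocol 8.2.5 a clinically significantly abnormal result prompts the repeat. If that result was scheduled, it stays in the table. The rule loses an extreme only when a non-technical repeat is worse than the first value, for example a QTcF of 470 ms followed by 505 ms (illustrative figures).
- **Scheduled-only tables give both arms the same measurement opportunities.** Adding discretionary values from an open-label study weakens that.

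The first three arguments hold the point to a minor one, but none supplies a count of participants per arm. The fourth is a good reason to keep the by-visit rows as they are. It is not a reason to omit a separate, labelled row.

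Two further inferences fail. The scheduled central-laboratory limit in SAP 5.1 concerns laboratory data, so the exclusion of off-schedule QTcF rests on 5.1.1.3 alone. And the general exclusion should not be read as removing unscheduled anti-drug antibody samples: SAP 5.1.1.2.3 sends those data to 5.5.1, where any positive post-Baseline measurement counts.

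**Conclusion.** The point holds as a minor, inexpensive improvement. Off-schedule and non-technical repeat post-dose values cannot enter the neutrophil or QTcF tables, and no table counts participants per arm with any post-dose extreme in either variable. The bioequivalence conclusion does not depend on this.

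The size is about 1.7 percentage points of an arm per affected participant, assuming a Safety Set arm of about 60. Few participants are likely to be involved, but with no event rate in the documents the total cannot be forecast. The conclusion also assumes that an Unscheduled Visit follows the default assessments. If the investigator advises otherwise, hematology or ECG may not be done.

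**What to change.** Keep all by-visit rows on scheduled values. Then:

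1. Add one worst-post-dose row per arm to the neutrophil shift table, using each participant's lowest valid post-dose central-laboratory value, whether scheduled, repeated or unscheduled. Local values stay in the listings, in line with SAP 5.1.
2. Add the same kind of row to the two QTcF category summaries, using the highest value and the largest increase from Baseline.
3. State that a value replaced by a technical repeat is not valid for these rows, and name the rows as an exception in SAP 5.1 and 5.1.1.3.
4. Footnote, per arm, how many participants have unscheduled values and how many are categorised only by one.

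The cost is one row in each of three tables, a footnote and a short exception, all from data already collected. Under the SAP Introduction this is a SAP amendment before database lock. After lock it is a supplementary analysis explained in the study report.

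The downside is that Unscheduled Visits are discretionary and the study is open-label, so the chance of detecting an extreme may differ by arm. The footnote lets a reader set aside the participants categorised only by an unscheduled value, but it does not correct the difference in detection.
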